**Statistical Analysis Plan**  
 Sponsor: Selecta Biosciences  
 Protocol No.: SEL-212/302

---

is permitted at any time between Day -7 to Day 0 inclusive. Uricase activity levels and sUA will be assessed through additional post-infusion blood samples at pre-determined time points by unblinded personnel. Also, anti-uricase and anti-pegadricase antibody levels will be assessed by unblinded personnel only in patients in active treatment arms. Antibody data will be saved in a project folder with restricted access by the unblinded team.

To maintain the blind, unblinded pre-specified medical personnel will adjudicate the implementation of the stopping rules.

### 3.7. Administration of Study Medication

#### Investigational Product and Placebo, Dosage and Mode of Administration:

##### Investigational Product

- SEL-212 is comprised of 2 components: SEL-110.36 and SEL-037
- SEL-110.36: nanoparticle composed of PLA and PLA-PEG encapsulating rapamycin
- SEL-037: pegadricase, a recombinant pegylated *C. utilis* urate oxidase

##### Dosage of Investigational Product

###### SEL-212A:

- SEL-110.36: 0.1 mg/kg based on patient's body weight
- SEL-037: 0.2 mg/kg based on patient's body weight

###### SEL-212B:

- SEL-110.36: 0.15 mg/kg based on patient's body weight
- SEL-037: 0.2 mg/kg based on patient's body weight

##### Mode of Administration

- Gout flare prophylaxis
  - Colchicine 0.6 mg oral (PO) every day starting at least 7 days prior to Day 0
    - Patients not already taking colchicine will receive colchicine 1.2 mg as a single loading dose followed by 0.6 mg daily as tolerated. If the patient cannot tolerate the loading dose level of 1.2 mg, then the patient will initiate and maintain colchicine at 0.6 mg per day. If the patient cannot tolerate the loading dose level of 0.6 mg, then the patient will initiate and maintain colchicine at 0.3 mg per day.
- Premedication (prior to study drug administration on Day 0 of each treatment period)
  - Prednisone (40 mg) orally approximately 24 ( $\pm$  12) hours prior to dosing
  - Fexofenadine 180 mg oral (PO) approximately 12 ( $\pm$  2) hours prior to dosing (i.e., the evening before dosing Day 0)
  - Fexofenadine 180 mg oral (PO) approximately 2 ( $\pm$  1) hours prior to dosing

This document is confidential.

**Statistical Analysis Plan**

Sponsor: Selecta Biosciences

Protocol No.: SEL-212/302

- Methylprednisolone 100 mg (or equivalent) up to 125 mg, depending on patient weight, IV 1 ( $\pm$  0.5) hours prior to dosing
- SEL-110.36
  - Blinded IV infusion with a syringe infusion pump at steady rate of 1.5 mL/hr for the first 30 minutes, then a rate adequate to deliver the remaining dose volume over a period of 60 minutes concurrently with normal saline. If an infusion reaction occurs during the administration of SEL-110.36, the infusion may be slowed, or stopped and then restarted at a slower rate at the discretion of the Investigator.
- SEL-037
  - Blinded administration beginning up to 30 minutes after completion of the SEL-110.36 infusion.
  - Blinded administration via infusion pump over no less than 120 minutes. If an infusion reaction occurs during the administration of SEL-037, the infusion may be slowed, or stopped and then restarted at a slower rate at the discretion of the Investigator.

**Placebo**

Placebo will consist of normal saline. Normal saline will be administered sequentially in the same way that the SEL-212B components are administered to maintain the integrity of the study blind. All pre-medications will be given prior to placebo as well to maintain the blind.

**3.8. Study Procedures and Flowchart**

Scheduled assessment are presented by the following 4 tables / appendices on the following pages:

- Table A: Schedule of Assessment
- Table B: Schedule of Assessments: Dosing, sUA, and Uricase Activity During the Treatment Phase
- Table C: Dosing, serum uric acid, and Uricase Activity Assessment Schedule (Treatment Periods 1, 2, 3, 4, and 5)
- Table D: Dosing, serum uric acid, and Uricase Activity Assessment Schedule (Treatment Period 6)

This document is confidential.

**Statistical Analysis Plan**  
 Sponsor: Selecta Biosciences  
 Protocol No.: SEL-212/302

**TABLE A: SCHEDULE OF ASSESSMENTS**

Assessment	Scr. - 45 d to D0 (Pre-dose) 	Treatment Phase														EOS 	ET	
		TP1 		TP2 		TP3 		TP4 		TP5 		TP6 						
		D0	D21 	D0 	D7 	D14 	D21 	D28										
Informed Consent	X																	
Demographics	X																	
Inclusion/Exclusion	X																	
Medical History	X																	
Chest X-Ray	X															X	X	
Multi-energy CT 	X							X								X	X	
Physical Examinations	X 	X 		X 				X 	X 									
Vital Signs	X	X 		X 		X	X		X									
Weight and Height 	X		X		X		X		X		X		X		X	X	X	
12-Lead ECG	X															X	X	
Screening Labs 	X																	
COVID-19 Testing	X																	
Urine Pregnancy Test	X																	
Washout: ULTs	X 																	
Document ULTs Discontinued	X																	
Dispense Premedication: Gout Flare and Infusion Reaction 	X		X		X		X		X		X		X					
Premedication: Gout Flare	X 																	
Randomization	X  <-----> X 																	
Premedication: Infusion Reaction		X 		X 		X 		X 		X 		X 						
Safety Labs: Chemistry 	X	X	X		X		X		X		X				X	X	X	
Safety Labs: Hematology 	X	X	X		X		X		X		X				X	X	X	
Safety Labs: Coagulation 	X	X	X		X		X		X		X				X	X	X	
Safety Labs: Lipids 	X	X	X		X		X		X		X				X	X	X	
Safety Labs: eGFR 	X	X	X		X		X		X		X				X	X	X	
Blood Sample for Anti-Pegadricase 		X	X	X	X	X	X	X	X	X	X	X			X	X	X	
Blood Sample for nAbs 		X	X	X	X	X	X	X	X	X	X	X			X	X	X	
Blood Sample for Anti-Pegadricase POC Validation 		X	X	X	X	X	X	X	X	X	X	X			X	X	X	
Blood Sample for Anti-Uricase 		X	X	X	X	X	X	X	X	X	X	X			X	X	X	
Blood Sample for Biomarkers 		X		X		X							X	X		X	X	
Blood Sample for Multiomic Markers		X		X		X		X		X		X	X			X	X	
Blood Sample for HLA Typing			X															
Blood Sample for T Cell Analysis		X											X	X		X	X	

This document is confidential.

**TABLE A: SCHEDULE OF ASSESSMENTS, CONTINUED**

Assessment	Scr. - 45 d to D0 (Pre-dose) 	Treatment Phase														EOS 	ET	
		TP1 		TP2 		TP3 		TP4 		TP5 		TP6 						
Day		D0	D21	D0 	D7 	D14 	D21 	D28										
Tophus Assessment/Photography	X							X								X		X
Gout Flare Assessment 	X	X	X	X	X	X	X	X	X	X	X	X	X	X	X		X	
Gout Flare Weekly Diary		Continuously on Weekly Basis 															X	
Joint Assessment (tenderness, swelling)		X						X								X		X
Health Questionnaires 		X					X									X		X
Collect Sample for sUA	X	Refer to Schedule of Assessments ( Appendix B ) for sUA Sample Collection during Treatment Phase															X	
PD/Uricase Activity Assessment		Refer to Schedule of Assessments ( Appendix B ) for PD/Uricase Activity Assessments during Treatment Phase															X	
Study Drug Administration		Refer to Schedule of Assessments in Appendix B for Study Drug Administration during the Treatment Phase																
Infusion Reaction Follow-up		Refer to Protocol Section 12.2.1.5																
Concomitant Medications / Procedures		Continuously														X	X	
AE Collection		Continuously														X	X	
SAE Collection		Continuously														X	X	

This document is confidential.

**Statistical Analysis Plan**  
 Sponsor: Selecta Biosciences  
 Protocol No.: SEL-212/302

---

1. Phone call at 30 (+4) days after the last study drug infusion for assessment of concomitant medications/procedures, AEs, and SAEs.
2. Visit window at Day 21 of each Treatment Period is +2/-1 days; visit window at Day 7 and Day 14 of Treatment Period 6 is +2/-1 days; visit window at Day 28 of Treatment Period 6 is +3/-4 days.
3. Visit window is -2 days.
4. Assessments at this visit are permitted to be performed remotely (inclusive of collecting applicable lab draws and assessments per protocol visit windows).
5. Study drug dosing to occur 28 days from the previous dose with a window of -4 days to +3 day of the intended dosing day. If a protocol deviation occurs where a patient is not able to be dosed within the dosing day window, for example in the case of COVID-19 restrictions temporarily preventing dosing, the current treatment period will be extended up to a maximum of 90 days without skipping doses for patients with a Day 21 visit sUA value  $\leq$  1.0 mg/dL during Treatment Period 1 or  $\leq$  6.0 mg/dL during Treatment Periods 2, 3, 4, or 5 in the D21 visit window or subsequent up to the rescheduled dosing visit. If a protocol deviation occurs in Treatment Period 6 such that the patient was unable to have an EOS visit performed within the visit window, then the Treatment Period 6 Day 28 visit should still occur 28 days (+3/-4 days) after the Treatment Period 6 dose or as close to the visit window as possible to collect the final primary endpoint SUA sample.
6. Assessment performed at select sites only
7. Full physical exam
8. Directed physical exam
9. Assess vital signs on Day 0 at Time 0 (pre-dose), within + 5 minutes after completion of infusion of the first component of study drug, and 1 hour (+ 5 minutes) after completion of infusion of the second component of study drug.
10. Height measured once during Screening only.
11. Screening labs to include: calcium, total complement, hemoglobin-A1c (HbA1c), hepatitis C antibody, hepatitis B surface antigen, human immunodeficiency virus 1/2 (HIV1/2), urinalysis, glucose-6-phosphate dehydrogenase (G6PD)
12. Dispense gout flare medication at Screening and as needed during the study. Dispense infusion reaction medication at Screening and at Day 21 of Treatment Periods 1-5.
13. Begin at least 7 days prior to Day 0 of Treatment Period 1.
14. Begin at least 7 days prior to Day 0 of Treatment Period 1.
15. Randomization is permitted at any time between Day -7 to Day 0 (prior to SEL-212 administration).
16. Premedication to minimize potential infusion reactions: oral antihistamines at 12 ( $\pm$  2) hours and 2 ( $\pm$  1) hours and IV steroids at 1 ( $\pm$  0.5) hours prior to study medication.
17. Chemistry labs to include: Alkaline phosphatase, alanine aminotransferase (ALT), aspartate aminotransferase (AST), Total Bilirubin, blood urea nitrogen (BUN), Creatinine, UACR, eGFR, Fibrinogen, Glucose (fasting), Electrolytes (sodium, potassium, chloride, bi-carbonate, phosphate, and magnesium)
18. Hematology labs to include: white blood cells (WBC) count with differential, Red blood cell (RBC) count, Hematocrit (Hct), Hemoglobin (Hgb), Platelet (Plt) count, and absolute neutrophil count (Abneu)
19. Coagulation labs to include: prothrombin time (PT), activated partial thromboplastin time (aPTT), international normalized ratio (INR)
20. Fasting lipid labs to include: total cholesterol, high density lipoprotein (HDL), low density lipoprotein (LDL), triglycerides
21. Collect samples prior to study drug dosing.
22. Gout flares assessed based on validated gout flare definition ([Gaffo 2018](#))
23. Start gout flare diary at Day 0 of Treatment Period 1.
24. Refer to [Protocol Section 11.3](#) for Health Questionnaires.

Abbreviations: CT: computed tomography; D (d): day; ECG: electrocardiogram; eGFR: estimated glomerular filtration rate; EOS: end of study; ET: early termination; h: hour; nAbs: neutralizing antibodies; PD: pharmacodynamic; RCTC: Rheumatology Common Toxicity Criteria; Scr: Screening Phase; sUA: serum uric acid; TP: treatment period; UACR: urine-albumin-creatinine ratio; ULT: urate lowering therapy

This document is confidential.

**Statistical Analysis Plan**  
 Sponsor: Selecta Biosciences  
 Protocol No.: SEL-212/302

[figure not shown]
**TABLE B:**  
**SCHEDULE OF ASSESSMENTS: DOSING, SUA, AND URICASE ACTIVITY DURING THE TREATMENT PHASE**

Assessments	Day Timepoint	Treatment Periods: 1, 2, 3, 4, and 5				Treatment Period 6							
		D0 				D0 				D7 	D14 	D21 	D28 
		0h	~1.5h	~3.5h	~4.5h		0h	~1.5h	~3.5	~4.5h			
Premedicate: Infusion Reaction		X 					X						
Blood Sample Uricase Activity		X 			X 	X	X 			X 	X	X	X
Blood Sample: sUA		X 			X 	X	X 			X 	X	X	X
Study Drug Infusion (Component 1) 		X-----X 					X-----X 						
Study Drug Infusion (Component 2) 			X  -----X					X  -----X					

[figure not shown]
1. Study drug dosing to occur 28 days from the previous dose with a window of -4 days to +3 day of the intended dosing day.
2. Assessments at this visit are permitted to be performed remotely (inclusive of collecting applicable lab draws and assessments per protocol visit windows).
3. Treatment Period 6 only.
4. Premedication to minimize potential infusion reactions: oral antihistamines at 12 ( $\pm$  2) hours and 2 ( $\pm$  1) hours and IV steroids at 1 ( $\pm$  0.5) hours prior to study medication.
5. Obtain sample prior to study drug infusion.
6. Obtain sample 1 hour (+15/-0 min) after completion of infusion of Component 2. If a patient is withdrawn from study drug, the post-dose uricase activity and post-dose sUA samples do not need to be collected.
7. Component 1 will be SEL-110.36 at 0.1 mg/kg for patients randomized to SEL-212A and SEL-110.36 at 0.15 mg/kg for patients randomized to SEL-212B or will be placebo.
8. Before starting infusion with Component 2, a period of up to 30 minutes is permitted after completion of infusion of Component 1.
9. Component 2 will be SEL-037 for patients randomized to either SEL-212A or to SEL-212B or will be placebo for patients randomized to placebo.

This document is confidential.

**TABLE C: DOSING, SERUM URIC ACID, AND URICASE ACTIVITY ASSESSMENT SCHEDULE  
 (TREATMENT PERIODS 1, 2, 3, 4, AND 5)**

**TABLE D: DOSING, SERUM URIC ACID, AND URICASE ACTIVITY ASSESSMENT SCHEDULE  
 (TREATMENT PERIOD 6)**

This document is confidential.

## 4. Endpoints

### 4.1. Primary Efficacy Endpoint

Each of the two active treatment groups, SEL-212A and SEL-212B, are compared to placebo with regards to the following primary endpoint:

- The percentage of patients who achieve and maintain reduction of sUA < 6 mg/dL for at least 80% of the time during Treatment Period 6 by Day 28

### 4.2. Secondary Efficacy Endpoints

#### Key Secondary Endpoints:

Each of the two active treatment groups, SEL-212A and SEL-212B, are compared to placebo with regards to the following key secondary endpoints:

- Reduction of mean sUA as computed by subtracting the Baseline sUA level from the mean sUA during Treatment Period 6
- Percent reduction of mean sUA as computed by subtracting the Baseline sUA level from the mean sUA during Treatment Period 6
- The change from Baseline to Day 28 of Treatment Period 6 in the physical summary score of the Short Form Health Survey (SF-36)
- In patients with tophi at Baseline, the percentage of patients with at least PR (as best response) in overall tophus response evaluation until Day 28 of Treatment Period TP6
- The percentage of patients who achieve and maintain reduction of sUA < 6 mg/dL for at least 80% of the time during Treatment Period TP6 by Day 28 in the subset of patients with tophi at baseline
- The change from Baseline to Day 28 of Treatment Period 6 in number of tender joints
- The change from Baseline to Day 28 of Treatment Period in the total score of the Health Assessment Questionnaire (HAQ-DI)
- Gout flare incidence during Treatment Periods 1-6
- Gout flare incidence during Treatment Periods 1-3

#### Additional Secondary Endpoints:

Each of the two active treatment groups, SEL-212A and SEL-212B, are compared to placebo with regards to the following additional secondary efficacy endpoints:

- Percentage of patients who achieve and maintain reduction of sUA < 6 mg/dL for 100% of the time during Treatment Period 6
- Number of pre-dose sUA values < 6 mg/dL during Treatment Periods 2-6 for each patient
- Pre-treatment anti-pegadricase and anti-uricase antibody formation and levels in each treatment period in the SEL-212 active treatment arms
- Percentage of patients with development of new tophi until Day 28 of Treatment Period TP6 in the subgroups of tophaceous patients and in non tophaceous patients at Baseline
- In patients with tophi at Baseline, the percentage of patients with at least PR (as best response) in overall tophus response evaluation until Day 0 of Treatment Period TP4

This document is confidential.

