Each of the two active treatment groups, SEL-212A and SEL-212B, are compared to placebo with regards to the following additional secondary efficacy endpoints:

- The percentage of patients who achieve and maintain reduction of sUA < 6 mg/dL for 100% of the time during Treatment Period 6
- Percentage of pre-dose sUA values < 6 mg/dL during Treatment Periods 2-6 for each patient
- Pre-treatment anti-pegadricase and anti-uricase antibody formation and levels in each treatment period in the SEL-212 active treatment arms during Treatment Periods 1-6
- Percentage of patients with development of new tophi until Day 28 of Treatment Period 6 in the subgroups of tophaceous patients and in non-tophaceous patients at Baseline
- In patients with tophi at Baseline, the percentage of patients with at least PR (as best response) in overall tophus response evaluation until Day 0 of Treatment Period 4
- Change from Baseline to Day 28 of Treatment Period 6 in subscales of Health Assessment Questionnaire (HAQ-DI), in Provider Global Assessment of Disease Activity, and in subscales of Short Form Health Survey (SF-36)
- The percentage of patients with at least 1 gout flare during Treatment Periods 1-3
- The percentage of patients with at least 1 gout flare during Treatment Periods 1-6
- Change from Baseline to Treatment Period 6 in number of swollen joints
- Length of time patients are anti-uricase antibody free or before induction of anti-uricase antibody levels above baseline in patients receiving SEL-212
- Length of time patients are anti-pegadricase antibody free or before induction of anti-pegadricase antibody levels above baseline in patients receiving SEL-212

Exploratory Endpoints:

- Levels of uricase activity in patients receiving SEL-212
- Levels of monosodium urate crystal deposits and/or total body monosodium urate crystal deposits (imaging patients only)
- Levels of inflammatory and tolerogenic biomarkers
- Changes in antibody production (anti-uricase and anti-pegadricase) in patients in the SEL-212 groups
- Gout flare incidence during Treatment Periods 4-6
- Gout flare incidence during Treatment Periods 1-3 based on self-reported weekly gout flare diary
- Gout flare incidence during Treatment Periods 1-6 based on self-reported weekly gout flare diary

- Gout flare incidence during Treatment Periods 4-6 based on self-reported weekly gout flare diary
- Assessment of association between multiomic markers of gout and treatment effect in patients treated with SEL-212

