6.2.2.2 Additional Secondary Efficacy Endpoints

Each of the two active treatment groups, SEL-212A and SEL-212B, are compared to placebo with regards to the following additional secondary efficacy endpoints:

- The percentage of patients who achieve and maintain reduction of sUA < 6 mg/dL for 100% of the time during Treatment Period 6
- Percentage of pre-dose sUA values ≤ 6 mg/dL during Treatment Periods 2-6 for each patient
- Pre-treatment anti-pegadricase and anti-uricase antibody formation and levels in each treatment period in the SEL-212 active treatment arms during Treatment Periods 1-6
- Percentage of patients with development of new tophi in the subgroups of tophaceous patients and in non-tophaceous patients at Baseline during Treatment Periods 1-6

- In patients with tophi at Baseline, the percentage of patients with at least PR (as best response) in overall tophus response evaluation until Day 0 of Treatment Period 4
- Change from Baseline to Day 28 of Treatment Period 6 in the subscales of Health Assessment Questionnaire (HAQ-DI), in Provider Global Assessment of Disease Activity, and in subscales of Short Form Health Survey (SF-36)
- The percentage of patients with at least 1 gout flare during Treatment Periods 1-3
- The percentage of patients with at least 1 gout flare during Treatment Periods 1-6
- Change from Baseline to Treatment Period 6 in number of swollen joints
- Length of time patients are anti-uricase antibody free or before induction of anti-uricase antibody levels above baseline in patients receiving SEL-212
- Length of time patients are anti-pegadricase antibody free or before induction of anti-pegadricase antibody levels above baseline in patients receiving SEL-212

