7.3 Treatment Assignment

Patients will be randomized in a double-blind way with an allocation ratio of 1:1:1 to receive treatment with two different dose levels of SEL-212 or placebo. Randomization will be stratified by presence/absence of tophi.

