13.4.3 Further Secondary Efficacy Endpoints and Analyses

Additional secondary efficacy endpoints will be summarized by treatment group using descriptive statistics on the ITT population and will be compared between each SEL-212 treatment group and placebo using MH considering the randomization stratum tophus presence (yes/no) in case of binary endpoints or using, or using continuity corrected Chi-square test in case of binary endpoints within subgroups with/without tophi at baseline. In case of continuous or numerical endpoints treatment groups will be compared by ANCOVA, or MMRM as appropriate. All tests – except the tests within

subgroups of tophus yes/no at Baseline - will adjust for the randomization stratum and will present exploratory p-values of two-sided tests. In addition, 95% confidence intervals for treatment differences between each SEL-212 treatment group and placebo will be computed. Details will be provided in the SAP.

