### 9.3.3. Additional Secondary Efficacy Endpoints and Analyses

- Percentage of patients who achieve and maintain reduction of sUA < 6 mg/dL for 100% of the time during TP6:

A frequency table of number and percentage of patients who achieve and maintain reduction of sUA < 6 mg/dL for 100% of the time during TP6 will be provided on the ITT population. Each SEL-212 treatment group will be compared versus placebo using the MH estimate and test for common risk difference considering the randomization stratum of tophus presence (yes/no) on the ITT population. In addition, 95% confidence intervals for treatment differences between each SEL-212 treatment group and placebo will be computed.

- Number with pre-dose sUA values < 6 mg/dL during TPs 2-6 for each patient:

A summary table of the mean number of TPs with pre-dose sUA values < 6 mg/dL during TP2 to TP6 will be provided by treatment group on the ITT population. Each SEL-212 treatment group will be compared versus placebo using ANCOVA model with the number of pre-dose values < 6 mg/dL during TPs 2-6 for each patient as dependent variable and treatment group as independent fixed effect variable. 95% confidence intervals for treatment differences between each SEL-212 treatment group and placebo will be presented.

- Anti-pegadricase and anti-uricase antibody formation and levels, pre-treatment for each treatment period in the SEL-212 active treatment arms:

Summary table of pre-treatment values of each variable will be provided by treatment period and by SEL-212 treatment group on the ITT population.

A descriptive summary table of D21 anti-pegadricase and anti-uricase antibody titers, D21 uricase activity values and D21 SUA values at each treatment period, stratified by treatment arm and whether or not the D21 SUA was above or less than or equal to the stopping rule level for that TP (i.e.  $\leq 1$  mg/dL in TP1 and  $\leq 6$  mg/dL in TPs 2-6).

- In patients with tophi at Baseline, the percentage of patients with at least PR (as best response) in overall tophus response evaluation until Day 0 of Treatment Period TP4

Pairwise comparison of each SEL-212 treatment group versus placebo will be performed using the Chi-square test with continuity correction. In addition, 95% confidence intervals for treatment differences between each SEL-212 treatment group and placebo will be computed.

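### For pre-dose sUA in TP2-6 the SAP analyses a count without the tophus stratum, the protocol specifies a stratum-adjusted percentage, and neither change is declared

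*SAP*

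**What the plan says.** **Protocol, endpoint.** The Synopsis has "Percentage of pre-dose sUA values < 6 mg/dL during Treatment Periods 2-6 for each patient". Section 6.2.2.2 has "Percentage of pre-dose sUA values ≤ 6 mg/dL during Treatment Periods 2-6 for each patient". Both are per-patient percentages. The thresholds differ, and neither text gives a denominator.

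**Protocol, analysis.** Section 7.3: "Randomization will be stratified by presence/absence of tophi". Section 13.4.3 says that tests of additional secondary endpoints, other than those within tophus subgroups, "will adjust for the randomization stratum and will present exploratory p-values of two-sided tests". It names ANCOVA or MMRM for continuous endpoints and leaves further detail to the SAP. Section 13 says that any modification of a planned analysis will be labelled as one in the final SAP.

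**SAP.** Section 4.2 has "Number of pre-dose sUA values < 6 mg/dL during Treatment Periods 2-6 for each patient". Section 9.3.3 says: "A summary table of the mean number of TPs with pre-dose sUA values < 6 mg/dL during TP2 to TP6 will be provided". The model there, labelled ANCOVA, takes the number of such values "for each patient as dependent variable and treatment group as independent fixed effect variable". No other term is named. Section 12 holds a single entry, the move from ANCOVA to ANOVA for the key secondary flare endpoints.

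**The concern.** There are two departures from the protocol on one endpoint, and neither is declared.

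First, a count has no denominator. If patients contribute different numbers of pre-dose samples, it can mix control of sUA with completeness of follow-up. SAP 7.3 plans imputation only for the primary and key secondary variables, and 9.3.3 gives no missing-value rule for this endpoint.

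Second, the model leaves out the factor used to stratify randomization, against an explicit protocol rule. An ANCOVA with no covariate and no stratum suggests an oversight.

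At stake is whether the reported result matches the endpoint and analysis that the protocol announced. No confirmatory claim depends on it: the endpoint is outside the hierarchy and carries exploratory p-values.

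**Working it through.** The documents give no sample size, power or result for this endpoint, so there is no stated figure to reproduce. The check compares the texts and then sizes each departure.

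**1. Is the missing stratum specific to this endpoint?** The other whole-population comparisons in SAP 9.3.3 keep it: the Mantel-Haenszel tests for sUA control 100% of the time and for patients with a flare, and the MMRMs for HAQ-DI subscales, SF-36 subscales, provider global assessment and swollen joints. Only this model lacks it.

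**2. Count against percentage.** Protocol Appendix B schedules one pre-dose sUA sample at Day 0 of each of TP2 to TP6, so five per patient. Let c be the number of values below 6 mg/dL and k the number obtained.

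- Percentage of scheduled = 100 × c/5 = 20c. This rescales the count, so the test result is identical.
- Percentage of obtained = 100 × c/k. This equals 20c only when k = 5 (or c = 0).

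| Obtained (k) | Below 6 (c) | SAP count | % of scheduled | % of obtained |
|---|---|---|---|---|
| 5 | 2 | 2 | 40 | 40 |
| 2 | 2 | 2 | 40 | 100 |
| 5 | 3 | 3 | 60 | 60 |
| 3 | 3 | 3 | 60 | 100 |

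**3. What unequal completeness could do.** Assume that each value obtained is below 6 mg/dL with probability 0.6 in both arms. One arm is complete; in the other, 30% of patients have only three values.

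- Mean count, complete arm: 5 × 0.6 = 3.00
- Mean count, other arm: 0.7 × 5 × 0.6 + 0.3 × 3 × 0.6 = 2.10 + 0.54 = 2.64
- Percentage of obtained: 60% in both arms
- Percentage of scheduled: 20 × 3.00 = 60% against 20 × 2.64 = 52.8%

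The gap of 0.36 values comes from missing samples alone. The inputs are illustrative; the documents do not give the missing rate by arm.

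**4. Leaving out the stratum.** Assumed inputs: two arms of 47, each with 28 tophaceous patients (about 60%, as planned) and 19 without tophi; residual SD 1.8 values; treatment effect 1.0 value; two-sided 5% test; stratum difference d from 0 to 1.5 values. With strata balanced across arms, the ratio of unadjusted to adjusted standard error is about √(1 + d² × p(1−p)/SD²), with p(1−p) = 28 × 19/47² = 0.241 and SD² = 3.24. A simulation of 2,000 trials per setting agrees:

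| d | Formula | Simulated SE ratio | Power without stratum | Power with stratum |
|---|---|---|---|---|
| 0 | 1.00 | 1.000 | 0.759 | 0.761 |
| 0.5 | 1.01 | 1.009 | 0.761 | 0.765 |
| 1.0 | 1.04 | 1.037 | 0.738 | 0.762 |
| 1.5 | 1.08 | 1.083 | 0.700 | 0.753 |

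Standard errors are about 0 to 8% too large, and power falls by about 0 to 5 points. The error is conservative.

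**5. Declaration.** SAP Section 12 mentions neither change. The revision history says that deviations from the protocol were added in version 1.1, so the list was open for editing and these two were not entered.

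**The case against.** The strongest reply is that the count may be the protocol's endpoint in other units. The protocol never says percentage of what. Over the five scheduled samples, the count loses nothing. This stands, and it limits the point. A reader might infer that two controlled values out of two obtained are 100% under the protocol and are wrongly equated with two out of five. That holds only if the denominator is the values obtained, which the documents do not state.

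The plan also limits missing samples. Patients withdrawn from study drug continue visits to the end of TP6 (Protocol 7.4.1.1). Appendix B waives only their post-dose samples. SAP 7.4 lets an unscheduled value stand in for a missing scheduled one. This stands in part. Study dropout and isolated missed samples remain: the protocol plans for about 8% early termination and added 15 + 20 = 35 patients for COVID-19 and conflict-related losses.

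Dividing by values obtained has its own bias. A patient who leaves after two controlled values scores 100%, and a patient with no values has no score. Counting a missing value as not controlled is close in spirit to the composite strategy of the primary estimand, although missing primary responses are themselves multiply imputed. Neither denominator is plainly right, so the choice has to be stated.

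None of this answers the missing stratum or the silence of Section 12. Leaving detail to the SAP does not cancel a rule that the same protocol section states outright.

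**Conclusion.** The point holds as an inconsistency between protocol and SAP with small consequences. The clearest part is the stratum: the SAP model breaks an explicit protocol rule that the neighbouring analyses follow. The cost is a modest loss of precision, and the 0 to 8% rests on the assumed SD and stratum differences. The change from percentage to count is real in wording and undeclared. It alters the test only if values are missing and the denominator is the values obtained.

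Two stronger readings are not supported. One is that the SAP necessarily analyses a different endpoint; with the denominator unstated, the documents cannot settle that. The other is that the model must include baseline sUA because it is called ANCOVA. Protocol 13.4.3 requires only the stratum, so baseline sUA is optional.

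The < 6 against ≤ 6 mg/dL conflict lies within the protocol. The SAP follows the Synopsis without comment. It affects only values of exactly 6 mg/dL.

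**What to change.** 1. In SAP 9.3.3, add the tophus randomization stratum to this model.
2. In SAP 4.2 and 9.3.3, restore the percentage and state its denominator, scheduled or obtained values. Give the other version as a sensitivity summary, and tabulate the number of values obtained by arm. If the denominator is the values obtained, say how a patient with none is handled. Alternatively, keep the count and enter the change with its rationale in SAP Section 12.
3. Reconcile the threshold between the protocol Synopsis and SAP (< 6 mg/dL) and Protocol 6.2.2.2 (≤ 6 mg/dL).

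The cost is SAP wording, one model term and one small table, plus a note or correction for the protocol threshold. No new data are needed, and no sample size or confirmatory test changes.
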